3.0 Objectives/Aims

Aim 1. Does an acute dose of suvorexant decrease reactivity to U-threat? H1: Relative to placebo, SUV will acutely dampen psychophysiological reactivity to U-threat, but not P-threat.

Aim 2. Does daily use of suvorexant decrease reactivity to U-threat? H2a: 4-weeks of SUV will result in greater reductions in psychophysiological reactivity to U-threat compared with placebo, and these changes will be specific to U-threat. **H2b:** SUV-related change in U-threat reactivity will be greatest amongst those with higher baseline U-threat reactivity. Exploratory: Daily SUV will similarly result in decreases in aINS and dACC reactivity and connectivity during U-threat relative to placebo, and brain change will correlate with startle change.

Aim 3. Does daily use of suvorexant change alcohol behavior, and is this change linked to brain-behavior U-threat change? H3a: Daily SUV will result in greater reductions in proportion of heavy drinking days (PHDD) and drinks per drinking day (DPDD). **H3b:** SUV-related changes in PHDD and DPDD will be greatest in those with higher U-threat reactivity. **H3c:** In all subjects, changes in alcohol behavior will correlate with changes in brain-behavioral U-threat reactivity.

Study duration. Participants will complete a Screening Session and three to five in-person laboratory sessions (dependent upon randomization) over the course of 1.5 – 2 months.

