Each morning for the 4-week medication trial period, subjects will be asked to complete a brief clinical assessment, sent directly to subjects' smartphones at 8:30am. The survey will capture: medication adherence (yes/no); timing of pill ingestion; time spent in bed and asleep; medication side-effects; number and timing of alcoholic beverages; alcohol craving; illicit substance use; mood; and new medication usage to monitor potential drug-drug interactions. If the survey is not completed, a reminder will be sent to the participant every 30 minutes for 150 minutes (5 total reminders). Responses will be collected, password-protected, and encrypted locally on smartphones.

Subjects who endorse medication side effects other than nighttime drowsiness will be contacted by the study physician for a review of symptoms and safety. Additionally, if subjects endorse taking new medications, the study physician will review the information and contact the subject if further information is needed. The study physician and PI will utilize Lexicomp to check drug-drug interactions and only interactions of minor severity will be allowed. Those found to have moderate or severe interactions will be withdrawn from the study, consistent with study exclusionary criteria.

Subjects will also be contacted if medication compliance falls below 80% or above 120%. At the final lab visit, subjects will be asked to bring their blister pack with them to verify compliance using the pill count method. Thus, medication compliance is tracked using both daily self-report, pictures, and objective pill count.

Post-Treatment Lab Visits. During the final days of the trial, subjects will return to the lab to repeat the lab protocol. Individuals enrolled in the BRAINS Group will come in for a separate visit to repeat the fMRI. At study conclusion, subjects will be debriefed and provided a list of AUD treatment referrals and resources.

Self-report Data Processing. All measures will be double entered, checked for discrepancies, and cleaned. Analyses will assume that 'missingness' occurred at random, with data imputed when necessary.

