12.0 Statistical Considerations

13.0 Aim 1. Does a single dose of SUV decrease reactivity to U-threat? Hypothesis

1: Relative to PBO, SUV will acutely dampen startle reactivity to U-threat, but not P-threat. We will conduct a multilevel mixed model with startle magnitude as the dependent variable. Startle to U-threat and P-threat will be included as a within-subjects factor, to test for specific changes in U-threat. Time (baseline vs. acute challenge) and treatment arm (SUV vs. PBO) will be included as within-subjects and between-subjects factors, respectively, and we expect a time x treatment arm x task condition interaction on startle. Models will include a random effect for participant.

14.0 Aim 2. Does daily use of SUV decrease reactivity to U-threat? Hypothesis 2a:

4-weeks of SUV will result in greater reductions in reactivity to U-threat compared with PBO, and these changes will be specific to U-threat. Hypothesis 2b: SUV-related change in U-threat reactivity will be greatest amongst those with higher baseline U-threat reactivity. Exploratory Analysis: SUV will similarly result in decreases in aINS and dACC reactivity and connectivity during U-threat relative to PBO, and brain change will correlate with startle change. For H2a, we will conduct a multilevel mixed model that is nearly identical to the model described for H1. However, the time variable will be modeled as baseline vs. post-treatment. For H2b,

we will include baseline startle to U-threat as a predictor in our model and test for a baseline startle by treatment arm interaction. Lastly, for our exploratory fMRI analyses, we will first extract activation and functional connectivity parameter estimates from anatomical aINS and dACC during U-threat (and P-threat) > No-threat contrast maps. fMRI variables will be tested as dependent variables in the model used for H2a. Magnitude of brain change will be directly correlated with magnitude of startle change.

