15.0 Aim 3. Does daily use of SUV change alcohol behavior, and is this change linked to brain-behavior U-threat change? Hypothesis 3a: Daily SUV will result in greater reductions in PHDD and DPDD compared with PBO. **Hypothesis 3b:** SUV-related changes in PHDD and DPDD will be greatest in those with higher U-threat reactivity. **Hypothesis 3c:** In all subjects, changes in brain-behavioral U-threat reactivity will correlate with changes in drinking behavior. For H3a, linear mixed models will be used to assess the impact of treatment arm (SUV vs. PBO) on changes in drinking behavior over the 4-week follow-up period (daily reports). If the assumptions of linear models are violated due to skewed residual errors, we will explore the use of Poisson and negative binomial generalized linear mixed models to model drinking behavior. For H3b, baseline startle potentiation to U-threat (and in secondary models, aINS, dACC, and BNST parameter estimates) will be entered as a covariate/predictor and we will test for a baseline startle to U-threat by treatment arm interaction on drinking behavior outcomes. Lastly, the hypothesis for H3c will be tested using a linear mixed model that includes magnitude of U-threat and P-threat reactivity (startle and brain, separate models), time, and treatment arm as predictors and PHDD and DPDD as the outcomes. We expect a startle by time interaction such that regardless of treatment arm, a change in U-threat reactivity will correspond to a change in drinking behavior.

Sample Size. Our key hypothesis testing involves treatment arm by session interactions on startle eyeblink potentiation. Assuming a medium to large effect size, which is supported by our preliminary data, a sample size of 40 individuals per treatment group would conservatively yield 91% power (a total sample size of 80 individuals). To account for potential screen-fails, participants requesting to drop out of the study, and the PI withdrawing participants due to meeting termination criteria, approval for 120 participants is requested.

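### The only fallback models named for PHDD in H3a are count models, the wrong family for a bounded proportion; in a change-over-time test they can widen standard errors, by an amount that depends on inputs the plan does not give

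*Combined protocol and SAP*

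**What the plan says.** Section 3.0 sets two drinking outcomes for H3a of different types: PHDD, a proportion between 0 and 1, and DPDD, an average count. Section 15.0 (Aim 3) analyses both under one specification: "For H3a, linear mixed models will be used to assess the impact of treatment arm" (suvorexant against placebo) "on changes in drinking behavior over the 4-week follow-up period (daily reports"). The fallback is conditional: "If the assumptions of linear models are violated due to skewed residual errors", then "we will explore the use of Poisson and negative binomial generalized linear mixed models to model drinking behavior". No binomial, logistic or beta-binomial model and no robust standard error is named for PHDD.

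The daily survey in section 6.0 collects "number and timing of alcoholic beverages" each morning of the 4-week treatment period, so PHDD rests on a yes/no value per reported day. The documents do not define a heavy drinking day and give no expected PHDD. They do not say whether the change in H3a is an arm-by-day slope, a pre-post contrast or an arm mean. The daily survey starts after the acute dose, and pre-treatment drinking comes from the Timeline Follow-back at Lab Visit 1 (Tables 1 and 2). The sentence "Models will include a random effect for participant" stands under Aim 1 only; no random-effect structure is given for H3a.

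**The concern.** A Poisson or negative binomial model suits a drink count. It does not suit PHDD, because it has no ceiling at 1 and assumes more within-person variance than a yes/no outcome can have. Adding up heavy days per week or per participant does not cure this, since the number of heavy days is still capped by the number of days reported.

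If the team moved PHDD to a count model and tested within-person change, the test could be conservative and lose power. Section 1.0 says the findings will inform and power a larger trial, so over-wide intervals on heavy drinking could carry forward into its design. The word explore also leaves the model family and effect scale (difference or rate ratio) open until outcome data are in hand.

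**Working it through.** **The plan's own figure.** The only power figure is 91%, with 40 per arm, for the arm-by-session interaction on startle. At two-sided 0.05 (assumed; no level is stated), a two-group comparison with 40 per arm has 61% power at d = 0.5, 91% at d = 0.74 and 95% at d = 0.8. So 91% fits a medium to large effect, but it says nothing about drinking. No H3a figure exists to reproduce.

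**Inputs.** From the documents: 40 per arm and about 28 daily reports per person. Assumed: heavy-day rate p from 0.15 to 0.65, participant SD 1.5 on the logit scale (1.0 or 1.2 where stated), and two-sided 0.05.

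**Step 1, closed form.** Poisson variance over Bernoulli variance is p / [p(1-p)] = 1/(1-p), so the standard error for a within-person effect is too large by 1/sqrt(1-p): 1.08 at p = 0.15, 1.20 at 0.30, 1.29 at 0.40, 1.41 at 0.50.

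If people differ in p around a mean m, the squared ratio becomes m / [m(1-m) - Var(p)], which is larger. At m = 0.5 with logit SD 1.5, numerical integration gives Var(p) = 0.073, and sqrt(0.5 / (0.25 - 0.073)) = 1.68. This is why the simulated ratios below exceed the simple formula.

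A negative binomial variance cannot fall below its mean, so on 0/1 data it is taken to collapse to Poisson; it was not fitted separately.

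**Step 2, simulation of the arm-by-time term.** Random-intercept models, no slope variation, 400 trials per setting. The ratio is mean model SE over the actual SD of the estimate, under no effect. The power columns use arm-by-time effects of -1.3, -1.05, -1.0 and -1.0 on the logit scale, chosen for the check and not taken from the plan.

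| p | Poisson SE ratio | Poisson false positives | Power: Poisson | Power: logistic | Power: linear |
|---|---|---|---|---|---|
| 0.15 | 1.14 | 3.3% | 65% | 81% | 82% |
| 0.30 | 1.44 | 0.7% | 55% | 84% | 85% |
| 0.40 | 1.60 | 0.5% | 44% | 86% | 86% |
| 0.50 | 1.72 | 0.3% | 36% | 85% | 86% |

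At p = 0.65 the ratio is 1.98. With participant SD 1.0 and p = 0.40 it is 1.47. Logistic and linear SE ratios under no effect were 0.95-1.06.

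**Step 3, individual slopes that differ (logit scale).**
- Poisson with a random intercept only, p = 0.40, slope SD 1.5: ratio 1.08.
- Further runs with participant SD 1.2: at p = 0.40, 1.42 with no slope variation, then 1.22, 1.02 and 0.91 at slope SD 1, 1.5 and 2; at p = 0.28, 1.34, 1.11, 0.95 and 0.83.
- Poisson with a random slope fitted (250 trials): 1.13 (p = 0.40, slope SD 1.5), 1.06 (p = 0.20, SD 1.5) and 1.01 (p = 0.50, SD 2.5). With no true slope variation, p = 0.40, it is still 1.46.

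**Step 4, arm difference in mean level.** The Poisson ratio is 0.92-1.01 for p from 0.30 to 0.65. At p = 0.40, power is 80% Poisson, 82% logistic and 79% linear. At p = 0.15 the ratio is 0.85, so the standard error is too narrow there (10.2% false positives).

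**Step 5, is a logistic model with only a participant intercept enough?** Not for a change term. Across the runs its false-positive rate was 9-11% at slope SD 1 and 14-19% at slope SD 1.5. The random-intercept linear model behaved the same way (16.0% at p = 0.40, slope SD 1.5). With a random slope fitted, the logistic model gave 4.8-6.0% when slopes varied, and 7.2% when they did not.

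**The case against.** The strongest reply is that the fallback is conditional and exploratory, and that the primary linear mixed model matched the logistic model in power (82-86%). That stands. A reader might infer that a real suvorexant effect on heavy drinking days is likely to be missed. The documents do not support this: the count models enter only if the linear model is judged inadequate, and no power is claimed for drinking.

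A reader might also take a fixed inflation, such as 30-70%, as a property of the plan. It is not. That range needs particular heavy-day rates, a change-over-time term and nearly parallel individual trends. The documents give none of these, and parallel trends are doubtful for drinking data.

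Nor can one say that the trigger will usually fire. No skewness cut-off is set. Skewness of a 0/1 outcome is (1-2p)/sqrt(p(1-p)): 1.96 at p = 0.15, 0.87 at 0.30, 0.41 at 0.40 and 0 at 0.50. Up to p = 0.5, the fallback is likeliest where the inflation is smallest.

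Count models are also reasonable for drink counts. But the sentence does not separate the two outcomes, so skewed DPDD residuals could carry PHDD into a count model too.

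**Conclusion.** The concern holds in a limited form. For PHDD the only named fallbacks are from the wrong family, and moving to them from the linear model offers no gain. If they are used for an arm-by-time test, with random-intercept models and little slope variation, standard errors are roughly 15-70% too wide for assumed heavy-day rates of 0.15-0.5. Power is then lower by 16 points at p = 0.15 (81 to 65) and by 49 at p = 0.50 (85 to 36).

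The excess falls to about zero, and can reverse, when individual slopes vary. There is no excess for the arm difference in mean level. The linear model is free of this variance-family problem, although leaving out a random slope would affect it as well. The family mismatch follows from the text; its size rests on a heavy-day rate, change term and random-effect structure that the documents do not state.

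**What to change.** In section 15.0:
- Replace the count-model fallback for PHDD with a binomial (logit) mixed model of the daily heavy-day indicator, or of heavy days out of days reported, with a participant random intercept.
- For any change-over-time term, add a random time slope or use participant-clustered robust standard errors. A logit model with a participant intercept alone is not safe for that test (Step 5).
- Report the arm effect as a marginal difference in PHDD, so that the scale is fixed in advance.
- Keep Poisson and negative binomial models for drink counts only.
- State the change term, the H3a random effects and the definition of a heavy drinking day on which the indicator depends.

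The cost is SAP wording and slightly more model fitting, on the same data. Random-slope models may fail to converge; if so, the robust standard errors serve as the pre-stated alternative.

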This multimodal design allows for a well-controlled test of whether an acute dose of SUV (Aim 1) and/or daily use of SUV (Aim 2) modifies brain-behavior targets of AUD dysfunction, particularly within individuals with high objective baseline stress reactivity. We will also examine whether daily SUV changes alcohol behavior, and whether this change in behavior is linked to brain-behavior change (Aim 3). Findings from this study will provide critical new knowledge regarding if and how orexin antagonism can be leveraged to treat AUD. The findings will also be used to inform and power a large-scale mechanistic clinical trial of SUV for AUD.

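### H3c estimates one U-threat–drinking slope pooled over both arms and assumes, without testing, that it is the same in each, so alone it does not answer the Aim 3 question about suvorexant

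*Combined protocol and SAP*

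**What the plan says.** Section 3.0 (Objectives/Aims) poses Aim 3 as "Does daily use of suvorexant change alcohol behavior, and is this change linked to brain-behavior U-threat change". Section 12.0 repeats the question, and the Project Summary (section 1.0) puts it in much the same terms. The change in question is the one that follows daily suvorexant.

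H3c is the part of Aim 3 that addresses the link. In section 12.0, under Aim 3, it reads "In all subjects, changes in brain-behavioral U-threat reactivity will correlate with changes in drinking behavior". Its linear mixed model takes the magnitude of U-threat and P-threat reactivity (startle and brain in separate models), together with "time, and treatment arm as predictors and PHDD and DPDD as the outcomes". One interaction is named, that of startle with time, and it is expected to be "such that regardless of treatment arm, a change in U-threat reactivity will correspond to a change in drinking behavior".

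The only arm interaction named under Aim 3 belongs to H3b. It uses baseline startle, not change in startle. No arm-specific slope and no mediation analysis is described.

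**The concern.** A main effect of arm lets average drinking differ between suvorexant and placebo. It does not let the relation between startle change and drinking change differ. The H3c result is therefore an average over two arms whose slopes are taken to be equal. The expected result is nevertheless worded as if equality across arms would be a finding.

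The H3b interaction does not fill this gap. It asks whether people with higher startle at baseline respond differently to the drug, not whether change tracks change under the drug.

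What is at stake is interpretation. The Project Summary says the findings will inform and power a larger mechanistic trial of suvorexant. A pooled link that comes mainly from the placebo arm could be carried into that planning as if it described participants on the drug, and nothing in the planned output would show the difference.

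**Working it through.** **Inputs from the documents.** 40 per arm, 80 in total (section 12.0, Sample Size); 20 per arm in the fMRI subset (section 2.0); the H3c model terms as above. Section 10.0 mentions Bonferroni correction, but no alpha, sidedness or family of tests is given for H3c.

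**Inputs assumed.** Two-sided alpha 0.05; drinking change regressed on startle change plus arm, a simplification of the planned mixed model; equal variances of change in the two arms; placebo correlation 0.4 to 0.6 and suvorexant correlation zero. The documents give no correlation.

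**The plan's own figure.** The 91% power refers to the arm by session effect on startle, not to H3c. With power = Φ(d√(n/2) − 1.96), n = 40 and d = 0.74, this is Φ(3.31 − 1.96) = Φ(1.35) = 0.91. The plan gives only a verbal effect size, so the figure cannot be reproduced uniquely. The conventional d = 0.5 gives 61% and d = 0.8 gives 95%, so 91% is compatible with the text. No power is stated for H3c.

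**What the pooled slope picks up.** With equal arms and equal variances, pooled r = (placebo r + suvorexant r)/2. A placebo-only r of 0.5 therefore appears as 0.25 in 80 people. The Fisher-z approximation is Φ(atanh(pooled r) × √(80 − 3) − 1.96), where √77 = 8.775. For 0.25 this is Φ(0.2554 × 8.775 − 1.96) = Φ(0.28) = 0.61.

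The simulated columns use 4,000 trials per row. For the two slopes, positive means significant in the predicted direction.

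| Placebo r (suvorexant r = 0) | Pooled r | Pooled test positive, Fisher z | Pooled test positive, simulated | Suvorexant slope positive, simulated | Arm by change term significant, simulated |
|---|---|---|---|---|---|
| 0.4 | 0.20 | 43% | 42% | 2% | 42% |
| 0.5 | 0.25 | 61% | 62% | 2% | 64% |
| 0.6 | 0.30 | 78% | 77% | 2% | 81% |

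The suvorexant-arm slope stays at its chance level (2.5% in the predicted direction). With 20 per arm, as in the fMRI subset, the pooled test is positive in 24%, 35% and 47%, and the interaction is significant in 24%, 35% and 50%.

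**What a per-arm slope can and cannot show.** Suppose the drug does nothing, but startle and drinking fluctuate together equally in both arms. The suvorexant-arm slope is then significant with probability Φ(atanh(r) × √37 − 1.96):
- r = 0.3: Φ(0.3095 × 6.083 − 1.96) = 47%
- r = 0.4: Φ(0.4236 × 6.083 − 1.96) = 73%

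Simulation gives 47–49% and 73–75%. A within-arm slope alone would therefore often credit an inert drug.

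**Precision.** The standard error of a one-arm slope relative to the pooled slope is √(80/40) = 1.41. For 80% power the interaction needs a Fisher-z difference of (1.96 + 0.8416) × √(2/37) = 0.651, that is r = tanh(0.651) = 0.57 in one arm against 0 in the other.

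**The case against.** The strongest reply is that the analysis matches its hypothesis. H3c is declared for all participants, and a pooled slope adjusted for arm is the direct test of that. Section 2.0 presents U-threat reactivity as a general negative-reinforcement mechanism related to drinking apart from any drug, which gives pooling a rationale. The comparative drug effects are tested in H2a and H3a. This stands: the pooled slope is not wrong and should remain.

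It also stands that the placebo-only case is extreme. Natural co-fluctuation would be expected in both arms. If the link were 0.5 on placebo and 0.25 on suvorexant, the pooled test would be positive in about 93% of trials, and correctly so, since a link exists in both arms. The interaction would then be significant in only about 22%.

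A further reply is that an arm interaction is unnamed, not excluded, because section 12.0 is written in shorthand. That is true as far as it goes. Under Aim 1, though, the shorthand names the highest-order interaction and leaves the lower-order terms implicit. Read the same way, H3c stops at startle by time.

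A reader might infer that the trial will report a positive H3c as proof of a link under suvorexant. The documents do not say so: the planned statement concerns all participants. U-threat's standing as a target also rests on earlier data and on Aims 1 and 2, not on H3c alone.

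**Conclusion.** The point holds as a gap between the Aim 3 question and the analysis offered for the link. The planned model assumes a common slope, so it cannot support the claim that the link holds whichever arm a person is in. Alone, it also does not show a link under suvorexant. This follows from the model structure and needs no assumed number.

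The size does rest on assumptions. With a placebo-only link of r = 0.4 to 0.6, 40 per arm, change scores and two-sided alpha 0.05, the pooled test is positive in about 42% to 77% of trials. A stricter alpha under the Bonferroni rule would lower these figures.

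Two stronger readings are not supported. The pooled test is not invalid for H3c as worded. Nor would the suvorexant-arm slope settle the drug question, because it is an observational correlation within one arm.

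The point is minor. Section 12.0 places the key hypothesis testing on arm by session effects on startle, and H3c is a correlational hypothesis within the third aim.

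**What to change.** - Keep the pooled slope as the H3c result for all participants.
- Prespecify, as a supporting analysis, an arm by U-threat-change term (startle by time by arm in the planned mixed-model form).
- Report the slope in each arm and the between-arm difference, each with a 95% confidence interval.
- State that the link holds across arms only alongside that difference and its interval.
- Treat the suvorexant-arm slope as necessary but not sufficient for any statement tied to the drug. Such a statement must also rest on the randomised arm effects in H2a and H3a.

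The cost is one model term and a few extra estimates from data already planned, with no added participants or visits. The drawback is precision: the per-arm slopes have a standard error about 1.4 times the pooled one, and the interaction reaches 80% power only near r = 0.57 against 0. The plan should therefore say that a non-significant interaction does not show the arms to be alike, above all in the fMRI subset.
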